6.3. Treatment Arm: Pediatric Asthma CHW Home Intervention

The pediatric asthma CHW home intervention is modeled after that of Krieger et.al.¹⁹ and refined from Project CURA.

6.3.1 Asthma Home Visit Protocol and Topics: Families will be offered 10 home visits over 12 months. At the CHW home visits, CHWs will spend 1-2 hours with the family. CHWs will educate them on the “core curriculum.” The topics in the core curriculum are standard topics for asthma educators and are intended to reduce impairment (prevent chronic symptoms, infrequent use of quick relief medications, maintain normal activity levels) and reduce risk (prevent exacerbations, minimize emergency care, prevent reduced lung growth, and minimize adverse therapy effects).¹³ The CHWs will approach each visit with the intention to teach one or two of the core curriculum topics. Each visit will begin with several minutes of social discussion for the purpose of relationship building. Behavior change plans from the previous visit will be reviewed and discussed. Behavior change plans are small goals for a specific change over a several-week period. Examples include: “getting a prescription from my doctor” or “writing down

when my child coughs". The main portion of the visit will involve the education session around a core curriculum topic. When a CHW notes a barrier in the delivery of the education, he or she will then incorporate a relevant self-management skill. For example, the CHW may know that the family is not giving a medication as often as prescribed but instead of just saying that, the CHW will have the family track how often the child is receiving their medication (self-monitoring). The family will "self-discover" they do not give the medicine as often as recommended. Then the CHW will have the family problem solve as to why that might be (storage location, parent work schedules, medication fear, etc.). Once they have a list of the problems, the family will create a behavior change plan for one problem they want to solve.

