6.4 Comparison Arm: Clinic-based AE-C Education

6.4.1 AE-C Training: Most candidates for the AE-C certification have prior experience as an asthma educator and therefore require only a preparatory course to pass the certification exam. Erie leadership will identify the appropriate candidate for this position. This person will then complete a 2-day comprehensive workshop offered in Chicago by the Respiratory Health Association (www.lungchicago.org/certified-asthma-educator-training/). If further training is required, an additional online course if available through the American Association of Respiratory Care (www.aarc.org/education/asthma_ course). Once this person has passed the AE-C certification exam, he/she will complete a subsequent 2-day training with the research investigators to familiarize him/her with the intervention expectations and protocol. The AE-C may start delivery of intervention before obtaining formal AE-C certification as long as they have completed a training course and the study-specific training.

6.4.2 AE-C Intervention Protocol: The AE-C will receive contact information and have access to the clinical chart for participants randomized to the AE-C arm. The AE-C will schedule the participant's family to come in for an educational session in the clinic. At this visit, the AE-C will assess and educate on asthma symptoms, control, triggers, medication technique, adherence, presence of a written asthma plan, and he/she will address caregiver/child concerns. The AE-C will call the family on the telephone in 2-4 weeks to discuss self-monitoring of symptoms and medication and answer any questions. The AE-C will schedule the participant's family again to come in for a similar visit at 6-months. A follow-up telephone call will occur 2-4 weeks later.

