9.0 Data Analysis

All analyses will be performed by the investigators and analysts in the Institute for Health Research and Policy using SAS version 9.4. We will compare key population descriptors in the two treatment groups as patient recruitment progresses (at N=100 and N=150) to ensure that the randomization process is achieving reasonable balance, being careful to protect operational staff from bias. Basic summary statistics will be calculated for outcome variables and covariates. Continuous variables will be assessed for normality using Q-Q plots and compared using 2-sample t-tests. If distributions are sufficiently non-normal, then a suitable transformation or non-parametric test will be used. Categorical variables will be compared using chi-square tests. Significance tests will be two-sided at level $\alpha=0.05$.

Specific Aim 1: To assess the efficacy of the integrated CHW home asthma intervention relative to the AE-C intervention at 12-months post-randomization as demonstrated by asthma control. This study will employ two primary measures of asthma control: number of days with activity limitation over the previous 14 days and the Asthma Control Test/childhood Asthma Control Test (ACT/cACT). The mean total number of days with activity limitation over the previous 14-day period will be assessed at 12-months between the two treatment arms using the two-sample t-test or Mann-Whitney test. If the mean days with activity limitation in the intervention arm is at least 30% lower than that of the AE-C arm and $p < 0.05$, we will conclude that the CHW intervention is more effective. The ACT/cACT will be analyzed using similar methods; a MID of 0.2 will be used to determine intervention efficacy. Linear mixed models will

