then be employed to analyze primary outcomes at twelve months. To test the CHW intervention's efficacy on these outcomes, we will first conduct per protocol analyses limited to those patients who received CHW intervention. We will correct potential selection bias by including covariates found to be differentially related to nonadherence. Under the missing at random (MAR) assumption, this ensures unbiased estimates from linear mixed models. Additionally, to test the intervention's effectiveness in clinical practice we will conduct intention-to-treat analyses that include outcomes for all patients randomized. Nonadherent and other subgroups of patients can be expected to exhibit differentially higher rates of missing data. We will therefore examine the sensitivity of inferences to multiple imputation rule using the SAS macros of Little and Yau (1996), including last observation carried forward (LOCF), return to baseline, and continuing on apparent trajectory. The fixed-effects part of the model will be $Days_{ij} = \beta_0 + \beta_1 Time_{ij} + \beta_2 Tx_i + \beta_3 (Tx_i * Time_{ij}) + \epsilon_{ij}$, for subject i at visit j . Candidate covariance structures will be assessed using the data's correlation structure and Akaike's Information Criterion (AIC). A random intercept will be included in the model if it significantly improves the model fit as determined by the likelihood ratio test. Standardized residuals and Cook's distance will be used to assess the influence of outliers and individual observations and residual plots will be used to check the multivariate normal distribution assumption. These analyses will be conducted in SAS PROC MIXED (and PROC GLIMMIX for categorical outcomes), and will be followed by an exploratory variable selection analysis in PROC GLMSELECT. Potentially confounding covariates will be considered for model inclusion using the least absolute shrinkage and selection operator (LASSO) model selection method. This method identifies a significant subgroup of covariates that will form a more parsimonious model. The LASSO method avoids problems typically encountered using stepwise procedures. To accommodate potential age-specific effects, heterogeneity of treatment effects by age will be examined as an exploratory analysis.

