Specific Aim 2: To assess maintenance of intervention efficacy, at 18 and 24 months after randomization. The asthma control measures will be compared between the two treatment groups at 18- and 24-months post-randomization as described above for Specific Aim 1. An indicator variable, to be named "Phase", will be added to the models to allow distinction between the time during intervention periods. The model will be: $Y_{it} = \beta_0 + \beta_1 Time_{ij} + \beta_2 Tx_i + \beta_3 (Tx_i * Time_{ij}) + \gamma_1 Phase_j * (Time_{ij} - 12) + \gamma_2 Tx_i * Phase_j * (Time_{ij} - 12) + \epsilon_{ij}$. We will conclude that any intervention effect is sustained if the slope for $\gamma_2 Time$ after 12-months continues to be positive in the CHW arm.

Specific Aim 3 compares the costs and cost effectiveness of the interventions. The analysis will be conducted from the societal perspective, including the costs borne by the program, individual participant and family, and healthcare system. 1) Cost and resource use information will be collected for the program, participant, and healthcare utilization. 2) Efficacy will be measured as asthma control as described for Specific Aim 1. 3) Cost effectiveness will be evaluated by combining the mean total cost per participant with change in asthma control. We will calculate the ICER for the CHW home intervention compared to AE-C services, such that $ICER_t = (C_1 - C_0) / (E_{1t} - E_{0t})$, where C is cost and E is effectiveness. Subscript 1 denotes CHW home intervention and subscript 0 denotes usual asthma care. t denotes the time period: 12 months, 18 months and 24 months. 95% confidence intervals for the ICERs will be calculated to evaluate the uncertainty in these results. 4) We will conduct one-way and multi-way sensitivity analyses for the key parameters to evaluate whether the ICERs are sensitive to plausible changes in their values. The sensitivity analysis is a check on the robustness and will determine the key parameters impacting the ICERs.

Specific Aim 4: To assess the efficacy of the integrated CHW home asthma intervention among those experiencing depression, stress, and/or PTSD. Interaction terms between treatment indicators for depression, stress, and PTSD will be examined to test for heterogeneity of treatment effects.

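### The mixed model for the 12-month outcomes assumes straight-line change, plans no check of it and names no 12-month contrast; one natural reading can misstate the 12-month difference by up to about 17%.

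*Combined protocol and SAP*

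**What the plan says.** Section 9.0 has two layers for Specific Aim 1. The first is a direct comparison: mean activity-limitation days "will be assessed at 12-months between the two treatment arms using the two-sample t-test or Mann-Whitney test". The success rule (at least 30% lower and p<0.05) follows immediately and belongs to that comparison.

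The second layer is the linear mixed models, which will "then be employed to analyze primary outcomes at twelve months". They carry the per-protocol and intention-to-treat estimates and the missing-at-random argument. Their mean structure is stated as "The fixed-effects part of the model will be $Days_{ij} = \beta_0 + \beta_1 Time_{ij"…, followed by one Tx term and one Tx-by-Time term. There is no visit factor and no curvature term.

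Specific Aim 2 extends the model with "\gamma_1 Phase_j * (Time_{ij} - 12" and its treatment counterpart. Subtracting 12 from Time shows that Time is a number of months, and the only change of slope allowed is at month 12.

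The covariance structure is left to AIC, and a random intercept to a likelihood ratio test. Residual plots are planned to check normality, and Cook's distance to check influence; nothing tests the linear mean. The plan does not say which function of the coefficients is the 12-month effect.

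On delivery, section 6.3.1 states "Families will be offered 10 home visits over 12 months". In section 6.4.2 the educator sees the family at the start and schedules them "again to come in for a similar visit at 6-months", with a follow-up call after each session.

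**The concern.** With visits at 0, 6 and 12 months, a single slope per arm means that each arm is assumed to change as much in the first half-year as in the second. The plan gives no time course of response that would support this. If the assumption fails, the fitted difference at month 12 is no longer an estimate of the difference at month 12. It also reflects what was happening at month 6.

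This matters because the mixed model is where the plan puts its intention-to-treat and per-protocol estimates. The plan relies on missing-at-random data for unbiased estimates from these models, but that also requires the mean model to be right. Leaving the contrast unnamed adds a second gap: two analysts could follow the text and report different 12-month effects from the same fit.

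**Working it through.** **Inputs.** Visit times 0, 6, 12, 18 and 24 months (section 6.2). Planning means (section 12.0): 3.9 days at baseline in both arms; at 12 months 2.84 (AE-C) and 2.00 (CHW). The month-6 difference is not given, so it is taken as a fraction f of the month-12 difference, with f from 0 to 1 (assumption). Write d0, d6, d12 for the arm differences at each visit.

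**The plan's own figure.** d12 = 2.84 − 2.00 = 0.84 days lower with CHW, and 0.84/2.84 = 29.6%, which matches the stated 30%. By the planning means d0 = 0. The plan gives no figure for error from the linear mean.

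**Weights for β2 + 12β3 (complete data; independence or compound symmetry).** The fitted slope of the differences is (d12 − d0)/12. The fitted value at month 12 is the average plus 6 months of slope:

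(d0 + d6 + d12)/3 + 6 × (d12 − d0)/12 = −(1/6)d0 + (1/3)d6 + (5/6)d12.

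**Size.** With d0 = 0 and d6 = f × d12, the fitted value is d12 × (5/6 + f/3), so the relative error is (2f − 1)/6.

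| f | Error | Fitted difference (planned 0.84) |
|---|---|---|
| 0 | −16.7% | 0.70 days |
| 0.5 | 0% | 0.84 days |
| 1 | +16.7% | 0.98 days |

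**Other covariance structures, same contrast, f from 0 to 1.**

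- AR(1): maximum error 13.0% (ρ = 0.3), 10.0% (ρ = 0.5), 6.5% (ρ = 0.7).
- Compound symmetry with 15% missing at month 12 (the plan's attrition rate, placed at that visit by assumption): about 20%.
- SDs falling over time (assumed ratios 2.2:1.6:1 or 2.2:1:1): about 6% to 20%.

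**Alternative contrast, 12β3.** With complete data under independence, compound symmetry or AR(1), the weights are −1, 0, +1. Month 6 drops out and, with d0 = 0, the error is zero. With 15% missing at month 12 the error reaches about 4%; under the assumed falling SDs it reaches about 24% to 47%.

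**Specific Aim 2 model.** Regressing the five differences on 1, t and max(t − 12, 0), with complete data and compound symmetry, the fitted 18-month difference is

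(−2d0 + 4d6 + 10d12 + 11d18 + 12d24)/35.

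Month 18 carries 11/35 = 0.31, against 0.34 for month 24, 0.29 for month 12 and 0.11 for month 6. Under AR(1) with ρ = 0.5, month 18 carries only 0.20.

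**Categorical visit.** With complete data the Tx contrast at month 12 is d12 itself: weight 0 on month 6 and 0.84 days whatever f is.

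**The case against.** A linear or piecewise-linear trend is a recognised choice, and several points on the other side stand.

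- **The success rule.** A reader might infer that the trial's 30% conclusion could be pushed to either side of its threshold. The documents do not support that: the rule is attached to the direct 12-month t-test or Mann-Whitney comparison, which uses no month-6 data, and it is nowhere applied to model-fitted means. Specific Aim 2 likewise refers back to the Aim 1 comparisons for months 18 and 24.
- **The schedules.** A reader might infer that the different delivery patterns show the response is not linear. They do not. AE-C gives a session and a call in each half-year, and the 10 CHW visits are not described as front- or back-loaded. Linearity is unsupported rather than contradicted.
- **The contrast.** Under the Tx-by-Time reading there is no error with complete data and equal variances. An inflated false-positive rate for a benefit present at month 6 and gone by month 12 also disappears on that reading. But the plan does not choose it, and it is not protected against missing data or unequal variances.
- **The size.** About 17% is the edge of a range, reached only if none or all of the effect is present at month 6. Compound symmetry is not the planned structure, since AIC decides.
- **Month-6 data.** The section 6.10 timeline labels the month-6 round as partial, and the visit marks in the outcome table cannot be read in the text available. If neither outcome is collected then, the Aim 1 problem does not arise.

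**Conclusion.** The point holds as a conditional and inexpensive improvement. The mixed model imposes an unchecked straight line over months 0 to 12 and leaves its 12-month contrast undefined. If the two outcomes are measured at month 6 and the effect is read as β2 + 12β3, the error is at most about 17% either way under independence or compound symmetry with complete data, assuming equal baselines and a month-6 difference between none and all of the month-12 difference. Under AR(1) with ρ from 0.3 to 0.7, the maximum falls from about 13% to 6.5%.

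The exposure is to the model-based per-protocol and intention-to-treat estimates, not to the direct 12-month test. The borrowing is heavier in Specific Aim 2, where less than a third of the weight for the fitted 18-month difference comes from month 18 under compound symmetry.

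**What to change.** In section 9.0, replace continuous Time in the mixed models with visit as a categorical factor (0, 6, 12; plus 18 and 24 for Specific Aim 2), with Tx-by-visit terms and an unstructured covariance. Name the Tx contrasts at months 12, 18 and 24 as the effects. State whether activity days and ACT/cACT are collected at month 6. Keep the linear and piecewise-linear models as a secondary description of trend. Month-6 data will still inform the 12-month estimate when month 12 is missing, but through the covariance rather than through an assumed line.

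The cost is one sentence in the plan and a CLASS statement in PROC MIXED. Specific Aim 1 goes from 4 fixed-effect parameters to 3 visits × 2 arms = 6, two more. If change really is linear, the standard error is slightly larger than the linear model would give.

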6.2 Design

This study employs a modified community-based participatory research (CBPR) approach. CBPR involves co-learning about issues of concern, reciprocal transfer of expertise, shared decision-making power, and mutual ownership of research products and processes.¹⁸ The proposed study leverages the resources and interests of each partner. Partners share control of study design, procedures, and outcomes. Erie will convene a Community Advisory Board (CAB), an internal group made up of patients and staff, on an as-needed basis, to advise the project team. In addition, the Chicago Asthma Consortium will function as our external advisory group. The Chicago Asthma Consortium Advisory Board will meet twice yearly. Major decisions on design, implementation, and dissemination will require approval of the CAB.

This study is designed as a behavioral randomized controlled trial. Child/caregiver dyads will be recruited and then randomized to one of two arms: CHW home visits, or education in the clinic from a certified asthma educator (AE-C). Intervention will be delivered in the first year of the study only. Data will be collected at baseline, 6, 12-months (post intervention), 18-months, and 24-months.

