6.10 Timeline

	Year 1	Year 2	Year 3	Year 4	Year 5
Instrument/staff preparation	■				
Recruitment		■	■		
CHW initial training		■			
Baseline data collection		■	■		
Active intervention		■	■	■	
6 month partial data collection		■	■		
12 month data collection			■	■	
Observation period			■	■	
18 month data collection			■	■	
24 month data collection			■		■
Data analysis			■	■	
Manuscript preparation			■	■	■

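### Aim 2's positive-slope rule does not measure maintenance: taken literally, a fully lost days benefit counts as sustained and an exactly held ACT/cACT benefit does not

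*Combined protocol and SAP*

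**What the plan says.** Section 3.0 hypothesises for Aim 2 that the gains are kept once the intervention stops; it does not hypothesise further growth. Section 6.2 confines the intervention to year 1: "Intervention will be delivered in the first year of the study only". Visits are at 0, 6, 12, 18 and 24 months.

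Section 9.0, Specific Aim 2, contains two things:

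- **A comparison at each late visit.** "The asthma control measures will be compared between the two treatment groups at 18- and 24-months post-randomization as described above for Specific Aim 1".
- **A decision rule from a model with a change of slope at month 12.** "We will conclude that any intervention effect is sustained if the slope for" γ2 Time "after 12-months continues to be positive in the CHW arm".

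Only the second is tied to the word *sustained*. The rule carries no margin, test or confidence limit, and no direction by outcome. It covers both primary measures. For days with activity limitation lower is better, since Aim 1 asks for a CHW mean "at least 30% lower than that of the AE-C arm". For ACT/cACT higher is better, since Section 4.1 treats a score below 20 as uncontrolled.

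**The concern.** In the stated model, γ2 multiplies treatment × Phase × (Time − 12). It is the change, after month 12, in the between-arm difference in slopes. It is neither a slope on Time nor the CHW arm's slope, so the sentence can be applied in at least three ways. Whichever is chosen, the sign of a slope says whether something is rising or falling. It does not say whether a gap is still there.

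The single sign adds a second problem. A rising line is bad news for days and good news for ACT/cACT. The Aim 2 report could therefore say *sustained* for days while the 24-month comparison in the same section shows no benefit, or *not sustained* for an ACT/cACT benefit kept in full.

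**Working it through.** **Inputs.** Section 12.0 days means: 3.9 at baseline in both arms; at 12 months 2.84 (AE-C) and 2.0 (CHW). Assumed, because the coding is not given: Phase = 1 after month 12 and Tx = 1 for CHW.

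**Before month 12.** AE-C slope = (2.84 − 3.9)/12 = −0.0883 per month. CHW slope = (2.0 − 3.9)/12 = −0.1583. So β2 = 0, β3 = −0.1583 + 0.0883 = −0.07, and the 12-month gap is 12 × (−0.07) = −0.84. The planned CHW days slope is already negative, so it cannot literally *continue* to be positive.

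**After month 12.** The arm difference is β2 + β3·t + γ2·(t − 12). At month 24 it is 24β3 + 12γ2 = −1.68 + 12γ2, so γ2 = (24-month gap + 1.68)/12.

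| Days, month 24 | Gap | γ2 | β3+γ2 | CHW slope, AE-C flat |
|---|---|---|---|---|
| Still widening at the same rate | −1.68 | 0 | −0.07 | −0.07 |
| Held | −0.84 | +0.07 | 0 | 0 |
| Half lost | −0.42 | +0.105 | +0.035 | +0.035 |
| Fully lost | 0 | +0.14 | +0.07 | +0.07 |
| CHW back at 3.9, AE-C at 2.84 | +1.06 | +0.228 | +0.158 | +0.158 |

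Taken literally, γ2 > 0 passes held, half lost and fully lost alike. The two slope readings do not pass a held benefit but pass a lost one. A CHW arm that ends worse than AE-C passes on all three. The γ2 and β3+γ2 columns do not depend on the AE-C trend; the last column does.

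**ACT/cACT (β3 > 0, β2 = 0).** Exactly held: the gap stays at 12β3, so γ2 = −β3 < 0 and β3+γ2 = 0; the CHW slope is 0 if AE-C is flat. None is positive. These signs need no SD and no ACT figures.

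**CHW arm's own slope.** It has no comparator. With assumed ACT/cACT means of 19 (AE-C) and 21 (CHW) at month 12 and both arms at 22 at month 24, the gap is fully lost, yet the CHW slope is (22 − 21)/12 = +0.083 and passes.

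**Positive read as favourable.** For days a pass then needs a negative value. Fully lost no longer passes. Held gives γ2 = +0.07 (wrong sign) and slopes of 0, so it still does not meet the rule.

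**Illustration, days fully lost.** Assumptions: 94 evaluable per arm (111 × 0.85); SD 2.06, back-solved as 0.84 × √(94.35/2)/(1.960 + 0.842); compound symmetry with correlation 0.2, 0.4, 0.6; complete data at all five visits. The documents give neither SD nor correlation. Generalised least squares gives:

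- SE(γ2) = 0.054, 0.046, 0.038. With γ2 = 0.14, the estimate is positive in over 99% of trials, and significantly positive at two-sided 5% in 74–96%.
- SE(β3+γ2) = 0.030, 0.026, 0.021. With 0.07, it is positive in 99% or more, and significantly positive in 64–91%.
- SE(24-month model contrast) = 0.279, 0.285, 0.290. Its 95% CI favours CHW in 2.5%, as it should when the gap is zero.

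Section 6.10 lists a "6 month partial data collection". Leaving month 6 out, the γ2 estimate is still positive in at least 99.5% of trials when the benefit is fully lost.

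**The case against.** The strongest defence is that *positive* means *favourable*. The mismatch with the planned negative days slope lends this some weight. A reader might infer from the table that a lost days benefit passes however the rule is read; the documents do not support that, because under the favourable reading it does not pass. What remains is that the rule then demands further improvement, which Section 3.0 does not hypothesise, and an exactly held benefit still does not qualify.

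Second, results for the CHW arm's own slope depend on the AE-C trend. If AE-C catches up while CHW stays flat, a lost days benefit gives 0 and does not pass; if both arms improve, a held ACT/cACT gap passes. So it would be wrong to say that both failures occur on every reading regardless of trend, or that the slope readings always catch a lost ACT/cACT benefit. This stands, and it is itself a reason not to use a slope without a comparator.

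Third, figures of 99% count only the sign of the estimate. Section 9.0 sets two-sided tests at 0.05 in general but attaches none to this rule. With a test, the chances fall to 64–96%, which is still far too high for a benefit that has gone.

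Fourth, the late between-arm comparisons are planned, so a lost benefit would be visible beside the slope statement. That is true and limits the harm. But the plan does not tie them to the conclusion or say which result prevails if they disagree.

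**Conclusion.** The concern holds: the only stated rule for *sustained* can give the wrong Aim 2 conclusion, and no reading of it measures maintenance as Section 3.0 hypothesises it. The literal failures (lost days benefit passes, held ACT/cACT benefit does not) are algebra under γ2 and β3+γ2, given the assumed Phase and treatment coding. Under the CHW arm's own slope they also need AE-C to stay flat. Under the favourable reading only the failure to recognise an exactly held benefit remains. The probabilities are illustrations that rest on an assumed SD, correlation and complete data.

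A reader might go further and infer that Aim 2 has no usable analysis, or that the primary aim is compromised. Neither follows: suitable between-arm comparisons at 18 and 24 months are already in the plan, and Aim 1 does not use this rule. It should be fixed before the Aim 2 analysis.

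**What to change.** 1. Delete the slope-sign rule.
2. State that the planned between-arm comparisons at 18 and at 24 months, each using that visit's data by the Aim 1 two-group method, govern the word *sustained*. Report them per outcome and visit with a 95% CI and the favourable direction: CHW lower for days, higher for ACT/cACT.
3. State whether Aim 1's added thresholds apply at these visits: the 30% reduction for days, and for ACT/cACT "a MID of 0.2 will be used to determine intervention efficacy". The choice matters. The planned days gap is 0.84/2.84 = 29.6%, so under the illustration's assumptions (normal data, AE-C mean 2.84) a fully held benefit at 24 months passes the t-test alone in about 79% of trials, and in about 48% with the 30% threshold added.
4. State that a CI excluding 0 shows that some benefit is still present, not that all of it is kept.
5. Keep the piecewise model as description. Define Phase, and report β3+γ2 with its 95% CI beside the 12-month contrast β2 + 12β3.
6. Do not let the model-based 18-month contrast govern, because the straight line can carry the 12-month gap forward. If the days gap grows linearly to −0.84 at month 12 and is zero at 18 and 24, the fitted 18-month contrast averages −0.29 and its CI favours CHW in 20–30% of trials, under the same assumptions.

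Cost: a few lines of SAP text, with no new data. The visit-specific comparison gives up some precision. For a fully held days benefit at 24 months it favours CHW in about 79% of trials, against 83–85% for the model contrast. The loss is larger at 18 months, where the model borrows from the visits on either side.

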3.0 Objectives/Aims

Primary Aim 1: To assess the efficacy of the integrated CHW home asthma intervention, relative to clinic-based AE-C education over 12-months, as demonstrated by asthma control. We hypothesize that the CHW arm will have significantly greater asthma control than the AE-C arm at 12-months as measured by days with activity limitation over the previous 14 days and the Asthma Control Test/childhood Asthma Control Test.

Specific Aim 2: To assess maintenance of intervention efficacy, as demonstrated by asthma control at 18 and 24 months after randomization. We hypothesize that changes in efficacy outcomes will be maintained after cessation of the intervention.

Specific Aim 3: To determine the cost-effectiveness at 12-months of CHW and AE-C intervention delivery, and additional costs or savings related to asthma exacerbations at 12- and 24-months.

Specific Aim 4: To assess the efficacy of the integrated CHW home asthma intervention relative to clinic-based AE-C education, as demonstrated by asthma control, among those experiencing depression, stress, and/or post-traumatic stress disorder (PTSD). We hypothesize that among those living with depression, stress, and/or PTSD, the CHW intervention will be significantly more effective in achieving and maintaining asthma control than the AE-C education intervention.

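### The ICER sets a total cost with no stated horizon against an effect read at the visit, so its denominator cannot register how long a benefit lasted

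*Combined protocol and SAP*

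**What the plan says.** Section 9.0, Specific Aim 3, builds the ratio in three statements.

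- Effect: "Efficacy will be measured as asthma control as described for Specific Aim 1". Aim 1 in the same section names two measures. One is the "number of days with activity limitation over the previous 14 days"; the other is the ACT/cACT score. Both are compared between arms at the visit.
- Combination: "Cost effectiveness will be evaluated by combining the mean total cost per participant with change in asthma control". Costs are societal, "including the costs borne by the program, individual participant and family, and healthcare system".
- Formula: "such that $ICER_t = (C_1 - C_0) / (E_{1t} - E_{0t})$, where C is cost and E is effectiveness". On the index: "t denotes the time period: 12 months, 18 months and 24 months".

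In the formula E carries the subscript t and C does not. Section 3.0 places cost-effectiveness at 12 months and adds "additional costs or savings related to asthma exacerbations at 12- and 24-months". Section 6.2 confines delivery of the intervention to the first year and schedules data collection at baseline, 6, 12, 18 and 24 months. Sections 3.0, 9.0 and 12.0 give no instruction to sum, average or integrate effect between visits.

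**The concern.** A cost-effectiveness ratio is interpretable when cost and effect refer to the same period. Here the numerator is a total whose period is not stated. The denominator is a reading at one visit, or the change in that reading since baseline. Neither form grows with the time for which a child has been better.

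This matters most at 18 and 24 months. The programme stops at month 12, so a benefit that persists adds limited days avoided at no further delivery cost. That is where maintenance should show its economic value, and the denominator as defined cannot show it. Conversely, a benefit present for most of two years but absent at the last visit leaves nothing to divide by. The 18- and 24-month ratios could not be read as a cost per day avoided over any defined period.

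**Working it through.** **Inputs.** Section 12.0 gives planning means for activity-limitation days per 14: 3.9 at baseline in both arms, and at 12 months 2.84 (AE-C) and 2 (CHW). The visit months come from Section 6.2. The documents give no incremental cost, no interim means and no ICER, so paths between visits and cost changes below are assumptions.

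**Planned effect.** 2.84 − 2 = 0.84 days per 14. Relative to AE-C, 0.84/2.84 = 29.6% (stated as 30%). Relative to baseline, 1 − 2/3.9 = 48.7% (stated as 50%). The planning figures reproduce to rounding.

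**Level or change makes no difference.** With equal baselines, the contrast in change is (3.9 − 2) − (3.9 − 2.84) = 1.90 − 1.06 = 0.84, the same as the contrast in level.

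**Days avoided.** There are 365.25/14 = 26.09 fortnights in a year. A difference of 0.84 held for a full year avoids 0.84 × 26.09 = 21.9 days. Days avoided to time t are the trapezoid area under the between-arm difference:

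- Linear from 0 to 0.84 over year 1: 0.5 × 0.84 × 26.09 = 10.96.
- Full effect by month 6: 0.75 × 0.84 × 26.09 = 16.44.
- No effect at month 6: 0.25 × 0.84 × 26.09 = 5.48.
- Year 2, held: add 21.91. Year 2, fading linearly to zero: add 10.96.

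| Assumed path of the difference | Plan's denominator at 12 / 24 months | Days avoided by 12 / 24 months |
|---|---|---|
| Linear to month 12, then held | 0.84 / 0.84 | 10.96 / 32.87 |
| Full by month 6, then held | 0.84 / 0.84 | 16.44 / 38.35 |
| None at month 6, full at 12, then held | 0.84 / 0.84 | 5.48 / 27.39 |
| Linear to month 12, fading to zero at 24 | 0.84 / 0 | 10.96 / 21.91 |
| Linear to month 12, zero at 18, back to 0.84 at 24 | 0.84 / 0.84 | 10.96 / 21.91 |

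The first and last rows give the same 24-month denominator, although days avoided differ by a third (32.87 against 21.91).

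**Effect on the ratio, linear-then-held path.**

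- Incremental cost constant, as the unindexed C implies. For an illustrative $1,000, the plan's ratio is 1,000/0.84 = $1,190 at 12, 18 and 24 months. Per day avoided over the period it is 1,000/10.96 = $91, 1,000/21.91 = $46 and 1,000/32.87 = $30.
- Incremental cost accumulating. If year 2 changes it by −50%, −20% or +20%, the plan's 24-month ratio is 0.50, 0.80 or 1.20 times its 12-month value. Matched over the period, days avoided triple, so these become 0.50/3 = 0.17, 0.80/3 = 0.27 and 1.20/3 = 0.40. In the last case the plan's ratio worsens by 20%, while cost per day avoided falls to 40% of its 12-month value.

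**The case against.** The strongest reply is that the plan is unspecific rather than wrong. The index is described as a time period, which could be meant cumulatively, and a cost per unit of control at a stated time is a legitimate, if less informative, ratio. Maintenance is tested separately under Aim 2. It is true that nothing rules out a cumulative intention. But no method for a cumulative effect is given, and the only measures referred to are visit-time ones, so the gap remains on either reading.

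Three stronger readings are tempting, and the documents do not support them:

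- A reader might infer that cost is accumulated to each of 12, 18 and 24 months. C has no time subscript, so its horizon is simply not stated.
- A reader might infer that a maintained benefit must leave the ICER unchanged. That holds only if incremental cost is the same at each t. Section 3.0 expects exacerbation costs or savings to be examined at both 12 and 24 months, so it may not be.
- A reader might infer that benefit between visits counts for nothing. It can enter the numerator through healthcare and family costs; it is absent only from E.

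Two further limits stand. The 14-day window belongs to one of the two Aim 1 measures; the documents give no recall window for ACT/cACT, though it too is scored at the visit. And the remedy rests on sparse data: four post-baseline fortnights, 56 days, would stand for about 730.

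**Conclusion.** The point holds in this form: ICER_t combines a cost with no stated horizon and a visit-time effect with no accumulation rule, so the denominator is insensitive to the duration of benefit. Under the planning difference and the linear-then-held path, it stays at 0.84 while days avoided triple from about 11.0 to 32.9. Across the other month-6 paths examined, the figures are 5.5 to 16.4 days by month 12 and 27.4 to 38.4 by month 24. If the effect fades towards zero by month 24, the ratio becomes unstable, and at zero it is undefined, although about 21.9 days were avoided.

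The denominator result needs no cost assumption. How far the ICER itself moves depends on incremental cost, for which the documents give no figure. All day counts rest on the assumed paths and on 0.84 being achieved.

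This should be fixed, but it concerns a secondary economic aim. The Aim 1 comparison and the sample size are unaffected.

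**What to change.** In Section 9.0, Aim 3, index cost as C_t and state that both C_t and E_t run from randomisation to t. For activity limitation, take E_t from the baseline-adjusted area under the curve, using trapezoids through months 0, 12, 18 and 24, and month 6 if the item is collected then. Scale each 14-day count to days and report cost per activity-limitation day avoided over 0 to t. Keep the 14-day value at t as a clinical outcome. For ACT/cACT, use the time-averaged score over 0 to t, or report it alongside costs as a consequence only.

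The cost is SAP wording and analysis effort on the planned visits. The downside is linear interpolation between widely spaced 14-day windows, which should be varied within the sensitivity analyses already planned for Aim 3.

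The sponsor should also state whether activity limitation is collected at month 6. The visit marks in the Section 6.8 outcome table were not legible in the text reviewed, and the Section 6.10 timeline calls that collection partial. Without month 6, the 12-month area is only a rescaling of the 12-month difference (0.5 × 26.09 = 13.04 times it), so the gain is mainly at 18 and 24 months.
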